The Food and Drug Administration has the authority to ban filter ventilation. However, we currently don't know what such a ban would do to consumption of unventilated cigarettes--that is, whether smokers would switch to unventilated cigarettes and demonstrate similar levels of consumption, or whether smokers would reduce cigarette consumption or quit entirely. We also do not know if such a ban would result in the substitution of other nicotine products (e.g., electronic cigarettes, cigarillos, etc.). One way of understanding the effects of ventilation bans on tobacco consumption is to investigate unventilated cigarettes as an inferior good. An inferior good is an inferior substitute for a preferred product. This can be established by manipulating the account balance of a cigarette smoker. A good is determined inferior if its consumption decreases as the account balance for tobacco products increases. Thus, in the present studies, we will examine the behavioral economic demand for unventilated cigarettes in participants who normally smoke highly ventilated cigarette varieties (i.e., "ultra light" and "light" cigarettes). Using an account balance we provide, participants will purchase ventilated and/or unventilated cigarettes in three separate sessions across a range of prices (e.g., \$0.12, \$0.25, \$0.50, \$1.00, \$2.00 per cigarette). For some participants, some participants may also have access to alternative nicotine products such as cigarillos, gum, or lozenges. Participants will be asked to make these purchases under six different account balance conditions. From each session, purchases from one price will be randomly selected and participants will take home all cigarettes purchased at that price. Participants will later return to the lab to return any unused cigarettes and receive reimbursement for these unused products.

Participants

Up to 160 smokers will participate in this study. To participate, smokers must:

- 1) provide written informed consent,
- 2) be 18-65 years of age,
- 3) be an active smoker,

- 4) report smoking daily in the past month,
- 5) have stable self-reported mental and physical health,
- 6) be willing to try unventilated cigarettes or alternative nicotine products.
- 7) report that their usual brand of cigarettes features >~20% filter ventilation (i.e., "ultra light" and "light" varieties).

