At each of two purchase sessions, participants will “purchase” two days’ worth of either the Marlboro Blacks or Golds in one session. Here, they will report the number of cigarettes they would like to purchase across increasing prices (e.g., \$0.12, \$0.25, \$0.50, \$1.00, \$2.00 per cigarette). In one session, the price of both ventilated and unventilated cigarettes will increase in tandem across trials. In the other session, only the price of ventilated cigarettes will increase across trials. They will complete this task 6 times at each session. Once with the account balance that reflects what they typically spend on tobacco products (100%). The full range of account balances will be 140%, 120%, 100%, 80%, 60%, and 40%. At the end of each session, one price from one of the six times they complete the task will be drawn randomly and the participant will take home all cigarettes purchased at this price. Participants may also complete hypothetical purchase tasks. For some participants, alternative nicotine products such as cigarillos, gum, or lozenges may be available as well in both the real and hypothetical purchase tasks.

In each of the purchase sessions, participants will be able to purchase as many cigarettes (or alternative nicotine products) as their account balance allows, with the total price of the products purchased deducted from their account balance. Participants will be informed that the price of any unused products that are returned to the laboratory at their next visit will be refunded to their account. Thus, the number of cigarettes used outside of the laboratory will be calculated from the amount that is provided minus the amount that is returned. Before and after each session, participants may be asked to complete product evaluation surveys to measure changes over the course of the study. Participants will also be asked to return used cigarette filters (and cigarillo butts, depending on their availability) following each purchase session and the sampling period in order to qualify for the next session so that we may detect tampering or alteration of our method of ventilation blocking.

Participants will also complete a series of computerized and/or paper assessments (see attached task files for examples) during the consent session, purchase, and/or follow-up sessions. Likewise, in all sessions, participants may also be asked to leave a urine sample. This sample may be tested for recent drug use and pregnancy, when applicable.

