InferiorGood-18-290

Behavioral Economic Methods for Assessing Tobacco Product Abuse Liability; Study 7

Statistical Analyses Plan

3/16/2018

Statistical Analysis Plan

The consumption results of the assigned cigarette purchased in the Electronic Tobacco Marketplace will be analyzed using the demand function (Koffarnus, Franck, Stein, & Bickel, 2015):

$$Q = Q_0 * 10^{k(e^{-\alpha Q_0 C} - 1)}$$

Where Q is consumption of the commodity, C is the price, Q_0 is the derived initial consumption without cost constraints (demand intensity), k is the span of the function in logarithmic units, and α is the demand elasticity. Q and C are determined by the data and k is set to a constant determined empirically by the actual data, leaving only Q_0 and α as free parameters to be fitted. Analysis will proceed by fitting the above equation to individual participant data, then comparing demand intensity and elasticity across time (through sessions) and between groups using mixed-effects modeling. A random effect will be included to model repeated measures on participants, and socio-economic and other demographic variables will be statistically screened for inclusion using model-based hypothesis tests.

In order to measure the substitutability of the unassigned cigarette, the consumption results of the unassigned cigarette purchased in the Electronic Tobacco Marketplace will be analyzed using the substitution function (Hursh and Roma, 2008):

$$Q = Q_{alone} * 10^{I * e^{-\beta C}}$$

In this equation, Q_{alone} represents the maximum consumption of the fixed-price commodity (e.g., assigned cigarette) when the primary commodity has a price high enough to drive consumption to zero, β is the sensitivity of fixed-price commodity consumption to the price of the primary commodity, I is an interaction parameter that indicates whether the fixed-price

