commodity is a substitute (positive β value), complement (negative β value), or independent (β value near zero) and Q and C represent consumption of the fixed-price commodity and cost of the primary commodity, respectively, and are known from date. This equation has three parameters (Q_{alone} , β , and β) that will be estimated from the experimental data using nonlinear regression. Analyses will proceed with the substitution equation being fit to individual subject data to generate subject-specific estimates of the maximum consumption, interaction, and sensitivity. These values will then be further analyzed to satisfy the goals of each experiment. Similar to the demand for the assigned cigarette, mixed model regression analyses will be used to include demographics and other covariates.

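### The SAP's substitution function uses price only and never account balance, so it cannot separate substitution from a balance effect, and the balance response that defines an inferior good has no planned analysis

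*SAP*

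**What the plan says.** **Design (Protocol, Procedures).** Participants complete a purchase task in which "they will report the number of cigarettes they would like to purchase across increasing prices", with example prices of $0.12, $0.25, $0.50, $1.00 and $2.00. Spending is capped by an account balance. One session moves both prices: "In one session, the price of both ventilated and unventilated cigarettes will increase in tandem across trials". The second fixes one: "In the other session, only the price of ventilated cigarettes will increase across trials". The level of the fixed unventilated price is not given. The task is repeated six times per session: "The full range of account balances will be 140%, 120%, 100%, 80%, 60%, and 40" per cent of usual tobacco spending.

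**Question (Protocol, Introduction).** A good counts as inferior when purchases of it fall as the balance rises. The same paragraph says "An inferior good is an inferior substitute for a preferred product".

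**Analysis (SAP, substitution function).** The stated aim begins "In order to measure the substitutability of the unassigned cigarette, the consumption results of the unassigned cigarette purchased in the Electronic Tobacco Marketplace". The function is Q = Q_alone × 10^(I·e^(−βC)). Its only regressor is C, the price of the other product, and "β is the sensitivity of fixed-price commodity consumption to the price of the primary commodity". The label comes from the sign of one parameter: "commodity is a substitute (positive β value), complement (negative β value), or independent (β value near zero". The individual estimates are then to be analysed further for the goals of each experiment, in mixed models with demographics and other covariates.

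Balance is in neither SAP equation. It is also not among the comparisons named for the demand parameters (sessions and groups) or the covariates named.

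**The concern.** In the fixed-price session a rise in the ventilated price does two things. It changes the relative price, and, if the balance is fully used, it leaves the participant able to buy less overall. If unventilated cigarettes are inferior, the second change alone pushes their purchases up. The fitted curve contains both effects.

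The direction matters because inferiority is the study's subject: if the hypothesis is right, the balance effect adds to the apparent substitution. If unventilated cigarettes are a normal good, it hides substitution. In addition, the quantity that defines an inferior good, the response to balance, has no analysis assigned to it, although a sixfold repetition of the task was built in to measure it.

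**Working it through.** The documents give no figure to reproduce here, so the check uses an identity and constructed data.

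**1. Identity (Slutsky).** Let U and V be unventilated and ventilated purchases, Pv the ventilated price and B the balance.

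- Gross effect: dU/dPv = compensated effect − V × dU/dB.
- So compensated effect = dU/dPv + V × dU/dB.
- If dU/dB < 0 (inferior) and V > 0, the gross effect exceeds the compensated one. If dU/dB > 0 (normal), it falls short of it.

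**2. Inferior-good illustration.** From the Protocol: the price grid and the balance percentages. Assumed: a smoker wants the equivalent of 40 ventilated cigarettes per two days, prefers ventilated, has a 100% balance of $12 (within the roughly $5 to $40 per session under Participant Compensation), and can buy unventilated cigarettes at $0.25, each counting as 1.5. When the balance binds and both are bought:

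U = (40·Pv − B)/(1.5·Pv − 0.25), V = 40 − 1.5·U.

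| Pv | $0.12 | $0.25 | $0.50 | $1.00 | $2.00 |
|---|---|---|---|---|---|
| U at B = $12 | 0 | 0 | 16 | 22.4 | 24.7 |

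At Pv = $0.50: U = 8/0.5 = 16 and V = 16. The slopes are dU/dPv = (40 × 0.5 − 1.5 × 8)/0.25 = 32 and dU/dB = −1/0.5 = −2. The compensated effect is 32 + 16 × (−2) = 0.

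In elasticities: the gross value is 32 × 0.5/16 = 1.0, the ventilated budget share is 16 × 0.5/12 = 0.667, and the balance elasticity is −2 × 12/16 = −1.5. So 1.0 + 0.667 × (−1.5) = 0.

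The SAP's function fits the five points with R² = 0.995 (I ≈ −27.6, β ≈ 10.2). That is three parameters on five points. Forcing I no lower than −5 still gives R² = 0.985, so only the rising shape is informative, not the size of I.

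**3. Different assumptions.** Take 40 wanted, a $10 balance, unventilated at $0.12 and one-for-one replacement, so U = (40·Pv − 10)/(Pv − 0.12). U is 0, 0, 26.3, 34.1 and 37.2. From $0.25 to $0.50 the rise is 26.3. With the balance raised to $20, so that the 40 ventilated stay affordable, the rise is 0.

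**4. Normal-good counter-case.** Assume a constant 70% of $10 goes on ventilated and 30% on unventilated at $0.12. U = 0.3 × 10/0.12 = 25 at every ventilated price, so the gross effect is 0. When Pv doubles, compensation takes the balance to $17 and U to 0.3 × 17/0.12 = 42.5. The gross 0 is +17.5 substitution and −17.5 balance effect.

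**5. Can the collected data separate the two?** In the case of step 2 at Pv = $0.50:

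| Balance | 40% | 60% | 80% | 100% | 120% | 140% |
|---|---|---|---|---|---|---|
| U | 19.2 | 25.6 | 20.8 | 16 | 11.2 | 6.4 |

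From 60% to 140% each $2.40 step changes U by −4.8, which is the slope of −2. At 40% no ventilated cigarettes are bought and U = 4.80/0.25 = 19.2, so the balance response need not be linear.

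Full compensation is also possible in places. At 80% ($9.60) and Pv = $0.50, U = 20.8 and V = 8.8. That bundle costs 8.8 × 1.00 + 20.8 × 0.25 = $14.00 at Pv = $1.00, or 117% of $12, and U at $14.00 is (40 − 14)/1.25 = 20.8, no change. At the unchanged $9.60, U rises to 24.3. By contrast, keeping 40 ventilated affordable at $0.50, $1.00 and $2.00 takes $20, $40 and $80, that is 167%, 333% and 667%, beyond the 140% maximum.

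**6. Sign rule.** dQ/dC = −ln(10) × Q × I × β × e^(−βC). Q_alone is described as the level reached when the other product's price is very high, which requires β > 0. Purchases then rise with price only if I < 0. With Q_alone = 40 and β = 1, I = −1 gives 5.2 rising to 29.3 over the grid, and I = +1 gives 308 falling to 54.6.

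**The case against.** - **A gross cross-price response is a legitimate meaning of substitute.** This stands. It fits the Protocol's own sentence, "An inferior good is an inferior substitute for a preferred product". The SAP does not say which meaning it uses, and that should be stated.
- **The illustrations assume what they show.** This largely stands. The two cigarettes serve the same need by construction, and zero compensated response follows from a strict preference. No document figure supports the 40 cigarettes, the $10 or $12, the fixed prices or the 1.5. The cases show what can happen, not what will.
- **The design already separates the effects.** This stands for the design: inferiority is tested by balance, over six levels, and the tandem session shrinks purchasing power while holding relative price constant if both prices move in proportion. It does not rescue the SAP, which assigns no analysis to either. The phrases about further analysis and other covariates could include balance but do not name it. A second-stage covariate on I or β would still not give a compensated price effect.
- **A compensated label would say little.** This stands. With two goods and a fully spent balance, standard demand theory does not allow a negative compensated effect, so complement could never be returned. The label should stay with the gross effect.

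A reader might go further and infer that the plan will call an inferior good a substitute when no true substitution exists, or that the two properties cannot be separated in this trial. The documents support neither. Zero compensated substitution is an assumed extreme, and the data needed for separation are collected.

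**Conclusion.** The point holds as a gap in the SAP. As written, the plan never estimates the response to balance that defines the study's subject, and it leaves a balance effect of unknown size inside I and β.

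That effect can account for none to all of a rise in unventilated purchases. It is zero where the balance does not bind or no ventilated cigarettes are bought, and it works against apparent substitution for a normal good. No size can be set from the documents; the constructed cases only mark the extremes.

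The conclusion rests on two readings. The first is that the unassigned cigarette is the unventilated one. The SAP does not define the term and gives the assigned cigarette as its example of the fixed-price product, so this is an inference. The second is that the balance limits purchases at the higher prices. At $2.00 a $12 balance buys six ventilated cigarettes, so this is plausible, but it depends on each participant's spending.

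The sign rule is a separate slip. Read as referring to I, it would call a rise in purchases a complement. The repeated β may come from typesetting or file conversion, but the direction of the rule needs correcting or confirming either way.

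**What to change.** In the SAP:

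1. Define assigned and unassigned in terms of the ventilated and unventilated cigarettes, and state the fixed unventilated price.
2. Model unventilated purchases in the fixed-price session jointly on ventilated price and balance, using all six levels and a participant random effect. Let the balance response vary with price and depart from a straight line, since it can turn at the lowest balances.
3. Base the inferior/normal conclusion on the balance slope.
4. State that the substitute, complement or independent label refers to the gross price effect at a given balance.
5. Report the balance-compensated effect, dU/dPv + V × dU/dB, as a secondary estimate with an interval (for example by bootstrap over participants), only for prices and balances within the 40% to 140% range. Use the tandem-price session as a supporting check.
6. Correct the sign rule: with β > 0, purchases rise with the other product's price only when I is negative.

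The cost is SAP wording and a little more analysis, with no new visits or data. The compensated estimate will be noisier than the gross one, which is a further reason to keep it secondary.

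### The SAP's assigned and unassigned cigarettes have no counterpart in the two-session protocol, and the substitution fit is not tied to the one session with a fixed-price cigarette, so own-price demand could be reported as a cross-product interaction

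*SAP*

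**What the plan says.** The SAP has two curve analyses. For the first, "The consumption results of the assigned cigarette purchased in the Electronic Tobacco Marketplace will be analyzed using the demand function". For the second, "the consumption results of the unassigned cigarette purchased in the Electronic Tobacco Marketplace will be analyzed using the substitution function". Neither assigned nor unassigned is defined.

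In explaining the second function, the SAP says that Q_alone "represents the maximum consumption of the fixed-price commodity (e.g., assigned cigarette"), and that "Q and C represent consumption of the fixed-price commodity and cost of the primary commodity". It classifies the result by a sign: the "commodity is a substitute (positive β value), complement (negative β value), or independent (β value near zero"). It names no session for either fit.

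The protocol (Procedures) describes two purchase sessions. In one, "the price of both ventilated and unventilated cigarettes will increase in tandem across trials". In the other, "only the price of ventilated cigarettes will increase across trials". The task is done six times per session, once for each account balance from 140% to 40%. In the protocol, being assigned refers only to conditions that add alternative nicotine products, not to a cigarette.

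**The concern.** An analyst cannot carry out the second analysis from these texts without choosing the product and the session. The labels do not map to ventilated and unventilated cigarettes. The rule and its example also point to different products: the function is fitted to the unassigned cigarette, yet the fixed-price good is illustrated by the assigned one.

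The choice of session matters because a cross-price function needs one price to stay still while the other moves. When both cigarette prices rise together, a fall in unventilated purchases cannot be separated into a response to its own price and a response to the ventilated price. Whether unventilated cigarettes act as a substitute bears directly on the protocol's question of what smokers would do under a ventilation ban. Two analysts following this SAP could choose different data and reach different answers.

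There is a related gap. However the labels are read, only one of the two cigarettes receives the demand function, although the protocol's Introduction sets out to examine demand for unventilated cigarettes in particular.

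**Working it through.** The documents give no figure to reproduce. The check has four parts.

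**1. Where a fixed-price cigarette exists.** Inputs from the protocol: five example prices, six balances, two sessions.

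| Session | Ventilated price | Unventilated price | Fixed-price cigarette |
|---|---|---|---|
| Tandem | rises | rises | none |
| Ventilated price only | rises | fixed | unventilated |

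Trials per cigarette per session: 5 × 6 = 30, so 60 over two sessions. Unventilated cigarettes are at a fixed price in 30 of 60 trials, ventilated cigarettes in 0 of 60.

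**2. How the two functions relate.** Expand the exponent of the demand function:

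Q0 × 10^(k(e^(-αQ0C) - 1)) = [Q0 × 10^(-k)] × 10^(k × e^(-αQ0C))

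The right-hand side is the substitution function with Q_alone = Q0 × 10^(-k), I = k and β = αQ0. Every demand curve is therefore also a substitution curve. This is exact and needs no assumed values.

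Worked example (assumed Q0 = 20, α = 0.01, k = 2):
- Q_alone = 20 × 10^(-2) = 0.2, I = 2, β = 0.01 × 20 = 0.2.
- At C = 1.00, the demand function gives 20 × 10^(2(e^(-0.2) - 1)) = 8.68.
- At C = 1.00, the substitution function gives 0.2 × 10^(2e^(-0.2)) = 8.68.

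Noise-free fits at 0.12, 0.25, 0.50, 1.00 and 2.00 over 36 assumed settings (Q0 of 5, 10, 20 and 40; α of 0.005, 0.01 and 0.02; k of 1.5, 2 and 3) all returned I = k with R² = 1.000. They confirm the algebra and add no evidence beyond it.

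**3. What pooling the sessions would do.** Three assumed settings were used (Q0, α, k = 20, 0.01, 2; 10, 0.01, 2; 20, 0.005, 2).

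| Fixed-price session, pooled with tandem data | Fitted I | R² |
|---|---|---|
| No cross-product effect (flat consumption) | 0.30 to 0.31 | 0.29 to 0.31 |
| True substitute, I = -0.8, β = 1.2 | -0.17 to 0.09 | 0.00 to 0.01 |

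So pooling could create an interaction where there is none, or nearly erase a real one. The low R² shows that something is wrong in a pooled fit, but not what. The perfect fit belongs to tandem data analysed alone. These pooled figures depend on the assumed values. With the fixed-price session used alone, the substitute case (Q_alone = 20, I = -0.8, β = 1.2) was recovered exactly.

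**4. The sign rule.** In the printed equation with β > 0, Q falls as C rises when I > 0 and rises when I < 0. A substitute therefore has negative I and a complement positive I. The SAP attaches positive values to substitutes and prints β as the symbol, although its text introduces I as the parameter that carries this meaning. The list of three parameters also prints β twice, so one β may be I lost in typing or text extraction.

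**The case against.** The strongest reply is that the SAP already limits the function through its variables: Q is consumption of a fixed-price good and C is the cost of another good. In the tandem session neither cigarette has a fixed price, so an analyst who follows those definitions has no tandem cigarette data to enter. This stands. A reader might infer that the SAP prescribes the wrong fit and that the artefact would be reported; the documents do not support that. The safeguard is only implicit, though, and the SAP's own example of the fixed-price good conflicts with the product it says it will fit.

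Other points also stand in part:
- The algebra shows what would happen if tandem purchases followed an ordinary downward demand curve. With both prices moving, and with unventilated cigarettes under study as a possible inferior good, that shape is not guaranteed.
- Procedures also contains an ambiguous phrase suggesting that one or the other cigarette is bought in a session. The price schedules that follow cover both cigarettes in both sessions.
- The Introduction mentions three sessions, and Participant Compensation separates a three-session Study 1 from a two-session Study 2. How Study 1 handled the cigarettes is not described, and the SAP's labels might fit it better.
- Some participants may buy cigarillos, gum or lozenges, and the protocol does not say that those prices rise. A fixed-price alternative could exist even in the tandem session, so the argument is confined to the two cigarettes.

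**Conclusion.** The concern holds for the two-session design as a gap and a contradiction in the SAP: undefined product labels, an example that conflicts with the rule, and no stated session for the substitution fit. The consequence is conditional. If tandem data enter the fit, own-price demand could appear as an interaction of size I = k, with no warning from the fit when tandem data are analysed alone. The identity is exact; the size of any distortion in a pooled fit rests on assumed parameters.

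Two further inferences should be resisted. A reader might conclude that the trial's main conclusion is at risk, but inferior-good status is judged by how consumption changes with account balance, not by this function. A reader might also conclude that the SAP's β sign rule would label every tandem curve a substitute. That rests on a symbol that is probably faulty and has to be checked in the source first.

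This should be fixed before analysis; it does not call the design into question.

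**What to change.** For the two-session design, amend the SAP as follows:
- Replace the assigned and unassigned labels: ventilated cigarettes (Marlboro Gold) are the primary commodity, and unventilated cigarettes (Marlboro Black) are the fixed-price commodity. Delete the parenthetical example in the definition of Q_alone.
- Tandem session: fit the demand function to each cigarette, noting that both prices move together, so the parameters describe a joint price response.
- Ventilated-price-only session: fit the demand function to ventilated cigarettes and the substitution function to unventilated cigarettes. Use the substitution function for the cigarettes in this session only.
- State separately how any fixed-price alternative products and the three-session Study 1 are handled.
- Check the repeated β against the source. If I is meant, make the sign rule match the printed equation: with β > 0, negative I for a substitute and positive I for a complement.

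The change is to wording and needs no new data or participants. Its only analytic cost is that the 30 tandem-session unventilated trials per participant are left out of the substitution fit; they remain in the demand analysis.

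### The SAP's sign rule for telling substitutes from complements is reversed for the equation it prints

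*SAP*

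**What the plan says.** The substitution-function paragraph of the SAP has a stated purpose: "In order to measure the substitutability of the unassigned cigarette". It gives the equation Q = Qalone × 10^(I·e^(−βC)), where Q is consumption of the fixed-price product and C is the price of the primary (other) product. It then gives each parameter a role:

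- Qalone "represents the maximum consumption of the fixed-price commodity", and the SAP ties this level to the situation "when the primary commodity has a price high enough to drive consumption to zero". That makes it the value approached at high C.
- β is defined as a sensitivity: how strongly purchases of the fixed-price product respond to the other price.
- The direction of the effect is given to the remaining parameter: "I is an interaction parameter that indicates whether the fixed-price". The sentence goes on to name three classes, namely substitute, complement and independent.

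The sentence about I ends with the sign rule: "commodity is a substitute (positive β value), complement (negative β value), or independent (β value near zero"). The symbol printed there is β, although the subject of the sentence is I. The list of fitted parameters that follows also prints β twice and omits I, yet the SAP goes on to promise "subject-specific estimates of the maximum consumption, interaction, and sensitivity". Neither document restricts the sign of I or β.

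**The concern.** The rule decides what the analysis is reported to have found. If it does not match the equation, an analyst who follows it exactly will call a substitute a complement, or the reverse.

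This function is the SAP's tool for substitutability. The Protocol (Procedures) has one purchase session in which only the ventilated price rises, which is the natural data for a cross-price curve. The Protocol's Introduction asks whether smokers would switch to unventilated cigarettes or to other nicotine products if ventilation were banned, so the direction of the cross-price effect bears on a motivating question.

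**Working it through.** **Inputs.** The equation and parameter definitions come from the SAP's substitution-function paragraph. The example prices ($0.12, $0.25, $0.50, $1.00, $2.00 per cigarette) come from the Protocol's Procedures section. The documents give no values for Qalone, I or β, so those below are assumptions for illustration.

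**Step 1: direction of the curve.** Differentiating,

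dQ/dC = −ln(10) · I · β · e^(−βC) · Q.

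Q, ln(10) and the exponential are all positive, so the sign of dQ/dC is the sign of −I·β.

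**Step 2: sign of β.** As C grows, e^(−βC) goes to zero, and Q to Qalone, only if β > 0. With assumed Qalone = 8 and β = −0.5, Q at C = $2.00 is 0.05 for I = −0.8 and 1,196 for I = +0.8. Neither is near 8, so the SAP's definition of Qalone needs β > 0.

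**Step 3: sign of I, given β > 0.**

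| I | Q as the other price rises | Meaning | SAP rule, read on I |
|---|---|---|---|
| negative | rises to Qalone | substitute | complement |
| positive | falls to Qalone | complement | substitute |
| zero | flat | independent | independent |

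The word maximum in the SAP's definition of Qalone agrees with this table. With β > 0, Qalone is the maximum only if I ≤ 0. If I > 0, which the rule calls a substitute, Qalone is the minimum.

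**Step 4: size.** At C = 0, e^0 = 1, so Q(0) = 10^I × Qalone for any β. With β > 0, Qalone is also the priced-out level, so 10^I compares the other product free with the other product priced out:

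- I = +0.3: 10^0.3 = 2.0 times as many when free (complement).
- I = −0.3: 10^(−0.3) = 0.50 times as many when free (substitute).

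Q at the Protocol's example prices, with assumed Qalone = 8 and β = 1.5:

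| I | $0.12 | $0.25 | $0.50 | $1.00 | $2.00 |
|---|---|---|---|---|---|
| −0.8 | 1.7 | 2.3 | 3.4 | 5.3 | 7.3 |
| +0.8 | 37.3 | 28.4 | 19.1 | 12.1 | 8.8 |

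For example, at $0.12 with I = −0.8: e^(−1.5 × 0.12) = 0.835, and 8 × 10^(−0.8 × 0.835) = 1.7.

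Over assumed |I| from 0.2 to 1 and β from 0.5 to 3, Q($2.00)/Q($0.12) runs from 1.30 to 6.10 for negative I and from 0.16 to 0.77 for positive I. Neither range crosses 1.

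**Step 5: fitting in the other direction.** Least-squares fits with β held non-negative, to invented purchases at the five prices:

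- Rising purchases 2, 4, 7, 12, 16 gave I = −1.09, β = 2.10, Qalone = 16.5.
- Falling purchases 16, 12, 8, 5, 4 gave I = +0.78, β = 1.71, Qalone = 3.7.

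The rule read on I labels both the wrong way round.

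**Step 6: the rule read literally on β.** By step 1, β alone does not fix the direction. At (I, β) = (−1, +1) Q rises, and at (+1, +1) it falls, with the same β. With the β > 0 that step 2 requires, the literal rule would call every product a substitute.

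**The case against.** The strongest reply is that the printed rule concerns β, and that the symbols in this paragraph are plainly unreliable, through the authors or the PDF reading. If I is negative, the literal rule works: β > 0 gives a rising curve, β < 0 a falling one, and β near zero a flat one. Qalone is then an upper bound for either sign of β. On that reading the rule is incomplete rather than reversed.

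This stands in part. Strict reversal depends on reading the rule as one about I, and the symbol should be checked against the original file. But the literal reading is the weaker one. The sentence is about I, and β has already been defined as sensitivity. The reading needs an unstated constraint on I, and its negative-β half contradicts the definition of Qalone. Neither reading gives a usable rule.

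Three smaller points also stand:

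- Treating Qalone as the priced-out level holds only for β > 0.
- The documents do not map assigned and unassigned onto ventilated and unventilated, so linking this function to the session where only the ventilated price rises is an inference.
- The consequence is limited. The mixed models use the estimates rather than the label, and the direction is visible in the raw purchases.

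**Conclusion.** The concern holds. Under the printed equation and the SAP's own definition of Qalone, negative I is a substitute and positive I a complement, so the stated rule is reversed for every nonzero I. This rests on algebra and on taking I as the classifying parameter, as the SAP's sentence does. The assumed parameter values only illustrate size. If β was meant, the rule is incomplete and conflicts with the definition of Qalone.

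The error can reverse the reported substitute or complement conclusion. It does not change the fitted curves, the parameter estimates, or the inferior-good criterion in the Protocol's Introduction, which depends on account balance. It should be fixed, but it does not threaten the design.

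**What to change.** In the SAP's substitution-function paragraph:

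1. State the rule on I, for β > 0: I < 0 is a substitute, I > 0 a complement, I near zero independent. Putting a minus sign before I in the equation and keeping the present wording for I would also work; do one or the other, not both.
2. Check the printed symbols against the original file and list the parameters "that will be estimated from the experimental data using nonlinear regression" as Qalone, I and β.
3. Either constrain β to be positive in the fitting, or say how a fit with β < 0 will be labelled, since Qalone then loses its stated meaning. Cover β near zero too: the curve is then flat whatever the value of I, so the sign of I should not be read as a direction.

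The cost is a few words in the SAP, with no change to design or data collection.
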